Treatment / Main Study Procedures	
Patients will be registered to receive pembrolizumab in combination with platin-based chemoradiotherapy. A pre-loading dose of 100 or 200mg (dependent on dosing level) of pembrolizumab will be given once the patient has completed the screening period. Patients will then return 2 weeks later to begin cycle 1 of a regimen of pembrolizumab 3 weekly at a dose of 100 or 200mg (dependent on dosing level) for a total of 7 cycles (3 during chemoradiotherapy and 4 after chemoradiotherapy).
 
Clinical assessments will be undertaken at the pre-loading dose and then every 3 weeks on the day on which the drug is administered. Patients will continue on this regimen until they complete all 8 doses of pembrolizumab, suffer disease progression, unacceptable toxicities, discontinue the study medication for any other reason or withdraw from the study. Chemoradiotherapy will begin with the cycle 1 dose of pembrolizumab and will continue for 35 fractions over a period of 7 weeks.
 
After the last dose of pembrolizumab patients will be expected to attend post-treatment follow-up visits as described below and/or safety follow-up (SFU) at 12 weeks or earlier if initiating a new anti-cancer treatment. Follow up requirements for patients are as follows:
 
 • If a patient completes all 8 doses of pembrolizumab without disease progression or unacceptable toxicities they will be seen at 4 weeks and 8 weeks after the last dose of pembrolizumab for the post treatment follow up. They will then return at 12 weeks for the SFU and after this be followed up every 4 weeks for 9 months to assess for disease status and the initiation of a new anti-cancer treatment. If the patient progresses or begins a new treatment during this time then they will move into the survival follow up every 12 weeks by telephone for overall survival until death, withdrawal of consent, or the end of the study • If a patient discontinues for reasons other than disease progression they will be seen at 8 weeks after the last dose of pembrolizumab for the post treatment follow up. They will then return at 12 weeks for the SFU and after this be followed up every 8 weeks for 9 months to assess disease status until progression, initiating a non-study cancer treatment or withdrawal. If a patient progresses or begins a new anticancer therapy patients will be followed every 12 weeks by telephone for overall survival until death, withdrawal of consent, or the end of the study. • If a patient progresses at any time in the study they would be expected to complete a SFU visit at 12 weeks after their last dose of pembrolizumab or before the initiation of a new anti-cancer treatment, whichever comes first. They will then move into survival follow up and will be followed every 12 weeks by telephone for overall survival until death, withdrawal of consent, or the end of the study. 
Patients will also undergo tumour assessment by RECIST 1.1 at screening, 8 weeks post chemoradiotherapy (cycle6) and then every 12 weeks for 12 months (irrespective of delays

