3.2 Treatment Regimen

All patients will receive radical platin-based chemoradiotherapy (70 Gy in 35 fractions plus cisplatin 100 mg/m² or carboplatin Area under the curve (AUC) = 5) on days 1, 22, 43 in combination with Pembrolizumab.

Pembrolizumab (at the dose level under current evaluation –100/200mg) will be administered as a pre-loading dose after the completion of the screening period, cycle 1 which will be 2 weeks after the pre-loading dose and then every 3 weeks for a total of 7 cycles (3 during chemoradiotherapy and 4 after chemoradiotherapy) or until disease progression, presence of unacceptable toxicities or withdrawal. Both the HPV-ve and HPV+ve arms will run simultaneously.

A minimum of 3 patients will be required per HPV cohort at each dose level. A minimum gap of 1 week should be left between the recruitment of the first and second patient in a new dosing level to mitigate against multiple patients suffering from any acute toxicity. If no dose limiting toxicity is observed in the first 3 patients at a dose level, pembrolizumab will be escalated to the next dosing level. If 1 in 3 patients experience a dose limiting toxicity then the cohort will be expanded to 6 patients. If 1 in 6 patients experience a DLT then the dose will be escalated to the next dosing level. However if ≥ 2 in 6 patients experience a DLT then the maximum administered dose (MAD) will have been reached and the previous dosing level, the MTD, should be used for the expansion phase. If $2/3$ patients experience a DLT the MTD will have been reached and the previous dosing level should be used for the expansion phase, if this occurs at dose level 1 the study would be stopped.

Once the MTD has been determined the trial enters the expansion cohort whereby a further 6 are treated in each HPV cohort with the determined dosage of pembrolizumab in combination with platin-based chemoradiotherapy.

[figure not shown]

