3.5.2 Post-Treatment Follow-up (A) Visit – Patients who complete all cycles of pembrolizumab

Patients who complete all cycles of pembrolizumab without disease progression or suffering unacceptable toxicities will be seen at 4 weeks and 8 weeks after the last dose of pembrolizumab. Procedures and assessments will be performed as defined in the schedule of study assessment (Table 2).

3.5.3 Post-Treatment Follow-up (B) Visit – Patients who discontinue without progression.

Patients who discontinue pembrolizumab for any reason other than disease progression will be seen 8 weeks after the last dose of pembrolizumab. Procedures and assessments will be performed as defined in the schedule of study assessment (Table 2).

3.5.4 12 Weeks Safety Follow-up (SFU) Visit

In addition to the above follow up all patients are expected to attend a mandatory safety follow-up visit conducted at 12 weeks after the last dose of pembrolizumab or before the initiation of a new anti-cancer treatment, whichever comes first. All AEs that occur prior to the safety follow-up visit should be recorded as described in section 7.0. After the safety follow-up any unresolved AEs at the patient's last visit should be followed up for as long as medically indicated, but without further recording in the CRF.

3.5.5 Post-Safety Follow-up (A) Visits – Patients who complete all cycles of pembrolizumab.

Patients who complete all cycles of pembrolizumab without disease progression or suffering unacceptable toxicities will move into the post-safety follow-up (A) phase. These patients will be assessed every 4 weeks from SFU for 9 months or until the patient suffers disease progression, they begin a new anti-cancer treatment or they withdraw. Each follow up visit will monitor disease status and assess for any new anti-cancer therapies. If a patient progresses or begins a new anti-cancer therapy they will move to the survival follow-up phase.

3.5.6 Post-Safety Follow-up (B) Visits – Patients who discontinue without progression.

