3.6 Study Termination

The end of the study is defined when the last patient has completed post-safety follow-up phase (A)/(B) or discontinued the study for other reasons.

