4.2 Registration

When the patient signs the consent form they will be allocated a trial identification number that will be used to identify the patient throughout the trial. Once all the screening assessments have been completed and the data entered on the CRFs; the patient will be assessed for eligibility. If eligible the patient will begin on the trial. If the patient is not eligible then the local investigator will make alternative arrangements for the treatment of the patient.

The trial ID will be a unique number that once assigned will become the permanent study identifier for that patient. In the event a patient is registered onto the study but does not begin treatment, then that patient's trial ID will not be reassigned. Treatment will begin within 3 days from the date eligibility has been confirmed. To ensure patient confidentiality patients will only be identified on CRFs, other trial specific forms and all communication to RM-CTU using their assigned trial ID. It is the PI's responsibility to maintain a confidential record of the identity i.e. full name and hospital number for the patients enrolled in this study and their assigned trial ID and date of birth. At the end of the study this record should be archived along with the Site File.

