6.3.7 Timing of Dose Administration

Trial treatment should be administered at the pre-loading dose and then on Day 1 of each cycle after all procedures/assessments have been completed as detailed in the Study Flow Chart (Section 3.4) and on the schedule of study assessment (Table 2). Trial treatment may be administered up to 3 days before or after the scheduled Day 1 of each cycle due to administrative reasons.

Cisplatin will be administered to the patient at a dose of 100 mg/m² with pre- and post-hydration as an in-patient. Therefore, the first 3 cycles of pembrolizumab will also be administered as an in-patient. Thereafter, all trial treatments will be administered on an outpatient basis. If the patient receives concomitant carboplatin (AUC = 5) rather than cisplatin, concomitant chemotherapy and study medication can be given as an outpatient.

Pembrolizumab will be administered as a 30 minute IV infusion (treatment cycle intervals may be increased due to toxicity as described in Section 6.3.9.2). Sites should make every effort to target infusion timing to be as close to 30 minutes as possible. However, given the variability of infusion pumps from site to site, a window of -5 minutes and +10 minutes is permitted (i.e., infusion time is 30 minutes: -5 min/+10 min).

The pharmacy manual contains specific instructions for pembrolizumab, reconstitution, preparation of the infusion fluid, and administration.

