8.2.2 Secondary Endpoints

1. To measure the PFS and overall survival at 6 months, 1 year and 2 years, respectively.
2. To measure the duration of clinical benefit using RECIST at 6 months, 1 year and 2 years, respectively.
3. To evaluate late radiotherapy toxicities as measured during treatment by LENT SOMA 52 weeks from the end of radiation therapy (week 7).

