8.2.6 Timing of analysis

For the primary end point, the results of each dosing level will be reviewed by the safety review committee (SRC) before recruitment to the next dose level can begin and once the MTD has been determined the trial enters the expansion cohort. Analysis of the secondary endpoints will take place 1 year after the enrolment of the last patient. Analysis of the exploratory endpoints will be reported once all the relevant samples have been collected and analysed.

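### Section 8.2.6 sets the secondary analysis about 8 to 13 weeks before the last patients reach the 52-week late-toxicity time point

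*Combined protocol and SAP*

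**What the plan says.** SAP section 8.2.6 gives a single trigger for all secondary endpoints: "Analysis of the secondary endpoints will take place 1 year after the enrolment of the last patient". It makes no exception for any of them and schedules no update.

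Section 8.2.2 (and 2.2.2 in the same words) defines the third secondary endpoint: "To evaluate late radiotherapy toxicities as measured during treatment by LENT SOMA 52 weeks from the end of radiation therapy (week 7". Section 8.2.5 plans to report late LENT SOMA effects as an incidence by highest grade. For PFS and OS it plans Kaplan-Meier estimates with censoring rules. For late toxicity it gives no rule for patients with incomplete follow-up.

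For patients who complete pembrolizumab, section 3.5.5 plans further visits after the 12-week safety follow-up (SFU): "These patients will be assessed every 4 weeks from SFU for 9 months". Section 3.6 ties the end of the study to that phase: "The end of the study is defined when the last patient has completed post-safety follow-up phase (A)/(B", or when the patient leaves for another reason. Section 10.11 plans a clinical study report at the end of the trial from final data listings.

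**The concern.** The analysis date is counted from enrolment and the endpoint's time point from the end of radiotherapy. Radiotherapy ends about two months after enrolment at the earliest, so a 52-week assessment counted from there cannot be complete one year after the last enrolment.

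At stake is the late-toxicity summary for the most recently enrolled patients. In a design that escalates first and expands last, these are likely to be expansion-cohort patients. Section 3.2 puts 6 of them in each HPV cohort and section 8.2.5 analyses the cohorts separately, so one or two patients with short follow-up make a visible difference. A highest-grade incidence that mixes about 43 weeks of observation with 52 weeks or more can miss late events but cannot add any, so the error runs towards under-counting. Section 1.2.3 names acceptable late toxicity among the study's aims.

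**Working it through.** **Inputs**

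- First dose to cycle 1: 2 weeks (section 3.2: "cycle 1 which will be 2 weeks after the pre-loading dose and then every 3 weeks for a total of 7 cycles").
- Radiotherapy: 7 weeks from cycle 1 (Trial Summary: "Chemoradiotherapy will begin with the cycle 1 dose of pembrolizumab and will continue for 35 fractions over a period of 7 weeks").
- Endpoint 3: 52 weeks after the end of radiotherapy, which 8.2.2 labels week 7.
- Trigger: 1 year = 365.25 / 7 = 52.2 weeks after the last enrolment.
- Eligibility to first dose (section 4.2): "Treatment will begin within 3 days from the date eligibility has been confirmed".
- Dosing window (section 6.3.7): "Trial treatment may be administered up to 3 days before or after the scheduled Day 1 of each cycle due to administrative reasons".

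**Check of the timeline against the plan's own figure.** Pre-loading dose to cycle 7 is 2 + 18 = 20 weeks. Adding 12 weeks to the SFU and 9 months (39.1 weeks) of post-safety visits gives 71.1 weeks, or 16.4 months. With an assumed 4-week screening period it is 17.3 months. Both lie within the 15-18 months of participation in the Trial Summary, so the week count matches the plan.

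**Gap between trigger and endpoint**

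| Reading of enrolment | Enrolment to endpoint (weeks) | Minus 52.2 |
|---|---|---|
| First dose, nominal | 2 + 7 + 52 = 61.0 | 8.8 |
| First dose, last fraction on day 46 and 3-day window used in full | 2 + 46/7 + 52 - 3/7 = 60.1 | 8.0 |
| Eligibility, 3 days before first dose | 61.0 + 3/7 = 61.4 | 9.2 |
| Consent, 4 weeks before first dose (assumption) | 61.0 + 4 = 65.0 | 12.8 |

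Every reading leaves a gap of about 8 to 13 weeks. Treatment delays would lengthen it.

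**Follow-up of the last patient at the trigger.** Time since the end of radiotherapy is 52.2 - (2 + 7) = 43.2 weeks if enrolment is the first dose. It is 43.2 - 4 = 39.2 weeks under the consent assumption.

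**Number affected (illustration only).** The documents give no accrual rate. The estimated 30 months' duration minus 16.4 months' participation leaves 13.6 months, or 59.3 weeks. Under even accrual the share enrolled in the last 8.8 weeks is 8.8 / 59.3 = 15%. Of the 24 patients on the shortest complete path (3 + 3 + 6 in each of two cohorts) that is 3.6, about 4. Of the maximum 36 it is 5.4, about 5.

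**Does planned follow-up reach the time point?** The endpoint is at week 59 from cycle 1. A completer has the SFU at week 18 + 12 = 30 and post-safety visits to about week 30 + 39.1 = 69, so the time point lies inside follow-up. A patient whose last dose is at cycle 3 (week 6), without progression, has the SFU at week 18 and ends post-safety follow-up (B) at about week 18 + 39.1 = 57, just short of week 59.

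**The case against.** Several points can be made for the plan.

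- **These patients still contribute.** A reader might infer that the last-enrolled patients drop out of the late-toxicity result, or are counted as free of toxicity at 52 weeks. The documents do not say so. Section 8.2.5 plans a highest-grade incidence, so every grade recorded up to about 43 weeks after radiotherapy counts. What is lost is roughly the last 9 weeks of a 52-week period, and the 52-week assessment itself. The endpoint wording is also unclear, since it speaks of measurement during treatment and then names a time long after treatment ends.
- **A later report is planned.** Section 10.11 bases the study report on final data listings, and sections 3.6 and 9.8 put the end of the trial after the 61-week point for completers. A reader therefore cannot conclude that the later data are discarded. But 10.11 does not schedule a second secondary analysis or amend 8.2.6, so the two sections need to be reconciled.
- **The number affected is uncertain.** Removing the waits for dose-limiting toxicity (DLT) review from the accrual period can push the share as high as 25-50% of all patients. A slow expansion phase makes it much smaller. Neither rests on an accrual rate in the documents. The gap in weeks needs no accrual assumption.
- **Late toxicity does not set the phase 2 dose.** This is correct. Section 3.1 carries forward the maximum tolerated dose, or 200 mg in the absence of DLT, and section 3.3 closes the DLT window 6 weeks after chemoradiotherapy. A reader who infers that the phase 2 dose decision is compromised goes too far.
- **The 2-year landmarks fail on the same sentence by more.** This is also true, but the present conflict would remain if those landmarks were dropped. Unlike them, it can be cured within planned follow-up for completers.

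**Conclusion.** The conflict is real and follows from the plan's own dates. Section 8.2.6 calls for the analysis of endpoint 3 about 8 to 13 weeks before the last patients reach its time point. The lower end uses the scheduling windows in full; the upper end assumes consent four weeks before first dose. Patients enrolled in that final stretch would lack the 52-week assessment and enter the highest-grade incidence with shortened follow-up, so late toxicity can be under-counted.

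The consequence is limited. It is truncated follow-up in a secondary, descriptive endpoint. Patients are not excluded, the primary endpoint is untouched and the phase 2 dose is not affected. About 4 of 24 or 5 of 36 patients is an illustration that depends on even accrual and on the estimated 30-month duration. That the affected patients come from the expansion cohort is likely from the order of recruitment, but not certain. The change is worth making because, as written, a named safety endpoint cannot be completed at its own analysis date.

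**What to change.** In 8.2.6, give endpoint 3 its own trigger: analyse it once every patient has had the LENT SOMA assessment at 52 weeks from the end of radiotherapy, or has died, progressed, withdrawn or completed scheduled follow-up. The last condition is needed for early discontinuers, whose visits can end at about week 57. The wording should name the visit or window that counts as the 52-week assessment. Alternatively, tie the analysis to the end-of-study definition in 3.6 and the final data listings in 10.11.

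If a 1-year analysis is kept, label its late-toxicity part interim, and report the number assessed at 52 weeks and the length of follow-up after radiotherapy.

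The cost is one sentence and a later result for this endpoint: about 9 to 13 weeks, or about 19 weeks (71.1 - 52.2 = 18.9, counting from first dose) if tied to the end of the study. No patients or follow-up visits are added. Early discontinuers whose schedule ends before week 59 would be reported with the follow-up they have.

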9.0 REGULATORY, ETHICAL AND LEGAL ISSUES

9.1 Good Clinical Practice

The study will be conducted in accordance with the guidelines laid down by the International Conference on Harmonisation for Good Clinical Practice (ICH GCP E6 guidelines).

9.2 Independent Ethics Committee (IEC) / Institutional Review Board (IRB)

9.2.1 Initial Approval

Before starting the trial, the protocol, patient information sheet, consent form, any other written information that will be provided to the patients and any advertisements that will be used and details of any patient compensation must be approved by the RM Committee for Clinical Research. Once approved, the study will then be submitted to the relevant Ethics Committee for their review and approval.

Prior to the shipment of IMP and the enrolling any patients the Investigator at each site is responsible for any site specific assessments and obtaining local R&D approval for the study

All participating sites will be required to sign an agreement with RM-CTU which includes requirement to sign and adhere to the trial protocol.

9.2.2 Approval of Amendments

Any protocol amendment should be agreed with the trial management group (TMG) and be approved by the sponsor prior to submission and review by the relevant Ethics Committee. Once favourable opinion from IEC has been obtained the amendment can be distributed to sites and implemented. It is the responsibility of the Principal Investigator to submit amendment to their R&D department for R&D approval Amendments requiring IEC approval may be implemented only after a copy of the IEC/IRB's approval letter has been obtained. Amendments that are intended to eliminate an apparent immediate hazard to patients may be implemented prior to receiving Sponsor or IEC/IRB approval. However, in this case, approval must be obtained as soon as possible after implementation.

9.2.3 Annual Safety Reports and End of Trial Notification

It is the responsibility of the sponsor to submit the Development Safety Update Report annually to the MHRA / REC on the anniversary of the studies MHRA/REC approval. This will facilitate the authorities continuing review of the study. These authorities will also be informed of the end of the study by the sponsor within 90 days of the trial completion. Copies of these reports will also be held within the main trial master file.

9.3 Regulatory Authority Approval

The study will be performed in compliance with UK regulatory requirements. Clinical Trial Authorisation (CTA) from the Medicines and Healthcare products Regulatory Authority (MHRA) will be obtained prior to the start of the study. In addition, the MHRA must approve amendments (as instructed by the Sponsor), receive SUSAR reports and annual safety updates, and be notified of the end of the trial.

9.4 Insurance and Liability

The Sponsors have secured indemnity from the manufacturer of pembrolizumab for patients in relation to adverse side effects for medicine-induced injury. Indemnity for participating hospitals is provided by the usual NHS indemnity arrangements for clinical negligence. A copy of the relevant insurance policy/indemnity scheme or summary shall be provided on request.

9.5 Contact with General Practitioner (GP)

It is the Investigator's responsibility to inform the patient's GP by letter that the patient is taking part in the study provided the patient agrees to this, and information to this effect is included in the PIS and ICF. A copy of the letter should be filed in the Site File. A template letter approved by the IEC/IRB will be provided by the Sponsor to all participating sites.

9.6 Patient Confidentiality

9.6.1 Patient Confidentiality and Data Sharing

The Principal investigator must ensure that the patient's confidentiality is maintained in compliance with the UK Data Protection Act of 1998. On the CRFs or other documents submitted to the RM-CTU, patients should be identified by their initials and a patient study number only.

In compliance with GCP guidelines, it is required that the investigator and institution permit authorised representatives of the sponsor and of the regulatory agency(s) direct access to review the patient's original medical records for verification of study-related procedures and data. Direct access includes examining, analysing, verifying, and reproducing any records and reports that are important to the evaluation of the study. The investigator is obligated to inform and obtain the consent of the patient to permit named representatives to have access to his/her study-related records without violating the confidentiality of the patient.

